#### 4.1 Informed Consent

A sample ICF and Assent Form with core information will be provided to each study site. Before study initiation at a given study site, each site/investigator must obtain a written approval/favorable opinion from its respective IRB/IEC for the ICF, assent form, and any other written information to be provided to participants. All ICFs and assent forms must be compliant with the ICH GCP guidelines and local regulations and must be approved by the Sponsor before submission to the IRB/IEC. The written approval of the IRB/IEC, together with the approved participant information, ICF, and assent forms, must be maintained in the study master files.

Written informed consent and/or assent must be obtained from a prospective participant and his/her parent/legal guardian before any study-specific procedures are performed on that individual. Participants who agree to participate in the study will sign the most recently approved ICF and/or Assent Form and will be provided with a copy of the fully executed document(s). The original, executed ICF and Assent Form will be maintained in the respective participant's clinical study file.

The ICF can be signed greater than 45 days before dosing and does not need to be re-signed before dosing unless specific reasons or local regulations apply (eg, a new consent version has been issued and approved by the IRB/IEC).

All screening imaging assessments must be performed within 21 days of C1D1, unless rescan by MRI or repeat photography is required.

# 4.2 Participant Discontinuation

Participants in the study will be removed from treatment or the study at any time if they meet any of the following criteria:

#### 4.2.1 Discontinuation From Treatment

- Participant experiences, in the opinion of the investigator, an acceleration of the overgrowth disease.
- Miransertib-related clinically significant toxicities that do not recover despite optimal treatment or dose reduction.
- Participant needs to take or elects to take another investigational agent.

• Development of any concurrent medical condition that might preclude or

contraindicate the further administration of miransertib.

- Serious protocol violations such as noncompliance with treatment or required follow-up and evaluation as determined by the investigator.
- Investigator's decision (in agreement with the Sponsor's Medical Monitor or designee).
- Participant, or guardian, refusal of further treatment/withdrawal of consent. Reasons for refusal of further treatment/withdrawal of consent should be noted in that participant's medical record.
- Death.

# 4.2.2 Discontinuation From the Study

- Participant and/or guardian refusal of further examinations (follow-up visits) and/or communications with the site/withdrawal of consent. Reasons for refusal/withdrawal of consent should be noted in that participant's medical record.
- Lost to follow-up.
- · Death.

# 4.3 Study Discontinuation

The Sponsor reserves the right to temporarily or permanently discontinue the study at any investigative site and at any time. Reasons for study discontinuation may include, but are not limited to, the following:

- Safety concerns
- Poor enrollment
- Investigator noncompliance with the protocol, GCP guidelines, or other regulatory requirements
- Request to discontinue the study by a regulatory or health authority
- Discontinuation of product development
- Manufacturing difficulties/concerns

The Sponsor and/or designee will promptly inform all Investigators and the appropriate regulatory authorities if the study is suspended or terminated for safety reasons. In the case of such termination, the investigator will notify their IRB/IEC.

#### 5 STUDY PROCEDURES

# 5.1 Medical History

Medical history will include but not be limited to the following:

- Demography: date of birth, sex, race and ethnicity
- Clinically significant prior diagnoses and surgical operations (not related to PROS or PS)
- Medications used within 45 days before the first dose of miransertib and throughout the treatment period should be reported
- Natural history of the disease (up to the study enrollment):
  - Perinatal history; prenatal and postnatal evaluations; family history; intellectual
    and psychomotor developmental milestones; disease-related manifestations
    (anatomical location, severity, frequency); management of the disease,
    including prophylactic and symptomatic therapies, hospitalizations, surgical
    operations; results of the clinical function assessments
- Genetic testing results: AKT1 or PIK3CA mutation status in the affected tissue must be confirmed before dosing. The AKT1 or PIK3CA mutation (dependent on clinical diagnosis) results will be captured in the EDC database and copies of the genetic report will be forwarded to the Sponsor or designee. If mutational status is unknown, archival or fresh tissue biopsy must be collected and tested for mutation status to confirm eligibility for the study.
  - An archival tissue sample is to be sent to the Sponsor or designee for central confirmation of mutation analysis, if required.
- When possible, imaging scans (eg, MRI, CT, US), photography, video recordings, and/or other assessments of size such as linear and/or circumference measurements performed before study enrollment will be collected and forwarded to the Sponsor or designee.

# 5.2 12-Lead Electrocardiogram

A 12-lead ECG will be conducted at specific timepoints (see Table 3 and Table 4). Additional ECGs may be conducted if clinically indicated or required per standard of care (triplicate if possible). The ECG parameters will be captured in the EDC database and copies of ECG tracings will be collected and forwarded for future analyses by the Sponsor or its designee.

#### **5.3** Clinical Laboratory Tests

Safety laboratory determinations will include hematology, blood chemistry, and urinalysis. Refer to the Schedule of Events (Table 3 and Table 4) of the protocol for testing frequency. All laboratory tests required for scheduled visits during the study must be obtained at the local laboratory at the investigational site. If laboratory tests need to be performed to assess an AE in between scheduled study visits, these tests can be performed at a laboratory close to the participant's home after agreement with the Sponsor.

Chemistry samples should be taken in a fasting state (fasting for at least 4 hours for children <6 years of age and at least 8 hours for children ≥6 years of age). If, in error, the participant has eaten ahead of testing, this should be documented as a fed rather than a fasting sample on the eCRF.

- Hematology: CBC including Hgb, hematocrit, white blood cell count with 5-part differential, red blood cell, platelet, and reticulocyte count
- HbA1c (screening only)
- Coagulation tests (screening only): PT, PTT, and INR, D-dimer and fibringen
- Blood chemistry: alkaline phosphatase, bicarbonate, calcium, phosphorus, magnesium, albumin, glucose, serum creatinine, and insulin
- Liver function tests: AST, ALT, LDH, alkaline phosphatase, total and direct bilirubin, uric acid, total protein, and BUN
- Electrolytes: sodium, potassium, and chloride
- Lipids: cholesterol, HDL, LDL, and triglycerides
- Routine urinalysis: dipstick and microscopy including protein, specific gravity, glucose and blood
- Serum pregnancy test for female participants of child-bearing potential, if applicable
- Clinical laboratory tests can be collected within 24 hours of CXDX clinic visit for all visits except C1D1.

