4.2.2 Baseline

Unless otherwise defined, baseline is defined as the last non-missing value (either scheduled, unscheduled or repeat) before the participant receives the first dose of miransertib.

Template: WCT-TP-ST-005-005

Page 8 of 24

Effective Date: 15-Apr-2016

Confidential

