4.3.7 Unscheduled Visits

Only scheduled post-baseline laboratory, vital signs, and ECG values will be tabulated. Post-baseline repeat/unscheduled assessments will be disregarded, although these post-baseline assessments will be listed in the relevant appendices to the CSR.

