4.17 Laboratory Data

Template: WCT-TP-ST-005-005 Page 18 of 24 Effective Date: 15-Apr-2016 Confidential

Descriptive statistics of the observed values and change from baseline (continuous data) will be presented by Part, Cohort, and treatment cycle for the following laboratory parameters:

- Hematology: complete blood count (CBC) including hemoglobin, hematocrit, white blood cell count with 5-part differential, red blood cell, platelet, and reticulocyte count
- Hemoglobin A1c (HbA1c)
- Coagulation tests (screening only): prothrombin time (PT), partial thromboplastin time (PTT), international normalized ratio (INR), D-dimer, and fibrinogen
- Blood chemistry: alkaline phosphatase, bicarbonate, calcium, phosphorus, magnesium, albumin, glucose, serum creatinine, and insulin
- Liver function tests: aspartate aminotransferase (AST), alanine aminotransferase (ALT), lactate dehydrogenase (LDH), alkaline phosphatase, total and direct bilirubin, uric acid, total protein, and blood urea nitrogen (BUN)
- Electrolytes: sodium, potassium, and chloride
- Lipids: cholesterol, high-density lipoprotein (HDL), low-density lipoprotein (LDL), and triglycerides

Each blood chemistry and liver function test parameter will be classed as below, within, or above normal range, based on ranges supplied by the laboratory used. Shift tables from baseline to the minimum post-baseline value and separately to the maximum post-baseline value will be presented by Part, Cohort, and overall.

The incidence of post-baseline ALT, AST, ALP, and total bilirubin values meeting CTCAE criteria will be summarized by Part, Cohort, and overall. Refer to Appendix 1 of this SAP for CTCAE definitions for these parameters. Additionally, the incidence of participants meeting Hy's law criteria will be summarized. Hy's law criteria are defined as follows:

- ALT ≥5xULN or
- ALP ≥2xULN or
- ALT ≥3xULN and total bilirubin ≥2xULN

For the third criterion which requires both an elevated ALT and elevated total bilirubin value, both lab values must be elevated at the same visit in order to be counted.

Template: WCT-TP-ST-005-005 Page 19 of 24 Effective Date: 15-Apr-2016 Confidential

The following laboratory parameters will be listed only:

- Serum pregnancy test for female patients of childbearing potential, if applicable
- Routine urinalysis: dipstick and microscopy including protein, glucose, and blood; pH, and specific gravity

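### The SAP never uses the fed-sample record, so a fed scheduled glucose can set a participant's shift category even when a fasting repeat exists

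*Protocol*

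**What the plan says.** Protocol 5.3: "Chemistry samples should be taken in a fasting state", with a minimum fast of 4 hours below age 6 and 8 hours from age 6. If the participant has eaten by mistake, "this should be documented as a fed rather than a fasting sample on the eCRF". Glucose and insulin are listed under blood chemistry; lipids are a separate group.

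SAP 4.17 gives observed values and change from baseline by cycle for each panel, including "Blood chemistry: alkaline phosphatase, bicarbonate, calcium, phosphorus, magnesium, albumin, glucose, serum creatinine, and insulin" and, as its own group, lipids. It then says "Each blood chemistry and liver function test parameter will be classed as below, within, or above normal range", using the laboratory's ranges, and "Shift tables from baseline to the minimum post-baseline value and separately to the maximum post-baseline value will be presented". Lipids are not among the classed parameters, so they have no shift table.

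SAP 4.3.7: "Only scheduled post-baseline laboratory, vital signs, and ECG values will be tabulated". It adds that "Post-baseline repeat/unscheduled assessments will be disregarded", although they are listed.

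SAP 4.2.2 takes as baseline the last available value before first dose, and a repeat or unscheduled value may count. It sets no fasting condition. SAP 4.3.5 (inexact values), 4.15 (safety analyses) and 7 (changes to planned analysis) do not mention fed samples either.

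**The concern.** The protocol sets a fasting condition and has sites record departures from it, but the analysis plan makes no use of the record. Two rules turn this from a missing detail into a possible wrong category. A maximum is decided by a single value. And a site that notices a fed draw and repeats it fasting does not correct the table, because the repeat is left out and the fed value stays.

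Glucose is where this matters. Hyperglycemia is the first risk named in Protocol 6.9. In the oncology study it was reported as drug-related in 5 of 28 participants on continuous dosing (Protocol Table 1). The SAP's CTCAE incidence table covers only ALT, AST, ALP and total bilirubin. HbA1c is measured at screening only (Protocol 5.3). Home fasting glucose, which Protocol 9.4 names as a safety assessment, is absent from SAP 4.15. The shift table is therefore the SAP's only categorical laboratory summary of glucose, and false shifts in it would overstate the drug's apparent effect.

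**Working it through.** The documents give no figure for this point, so there is none to reproduce. The check has two parts.

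**1. Following the rules as written.** Suppose a scheduled glucose is drawn fed, exceeds ULN and is repeated fasting with a normal result, and every other scheduled value is normal.
- SAP 4.3.7 keeps the scheduled value and drops the repeat from the tables.
- SAP 4.17 takes the maximum, which is the fed value, and classes the participant as above normal.
- The fasting repeat appears only in a listing.

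**2. How often this could happen.**

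Number of scheduled post-baseline draws, *k*:
- *Fasting clinical blood tests, Protocol Table 3 (Cohorts 1-3), full schedule:* C2, C3, C5, C9, C11 (5) + C4D1 (1) + C7, C13 (2) + C16 to C46 every third cycle (11) + end of treatment (1) + 30-day follow-up (1) = 21. Protocol section 4 describes the same visit pattern.
- *Separate insulin/glucose row, Table 3:* C7, C13, C19, C25, C37 and end of treatment = 6.

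Protocol 5.3 places glucose in routine chemistry, which supports 21 for glucose. It places insulin there too, although insulin has the sparser row. The documents do not settle this, so both counts are shown.

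Assumptions not in the documents:
- *f* = share of draws that are fed: 1%, 2%, 5%.
- *q* = chance that a fed glucose exceeds ULN: 25% to 75%.
- Draws are independent.

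Formulas:
- At least one fed draw: 1 − (1 − *f*)^*k*
- False above-normal shift in a participant whose fasting values are all normal: 1 − (1 − *fq*)^*k*

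| *k* | *f* | Any fed draw | False shift, *q*=25% | *q*=50% | *q*=75% |
|---|---|---|---|---|---|
| 21 | 1% | 19.0% | 5.1% | 10.0% | 14.6% |
| 21 | 2% | 34.6% | 10.0% | 19.0% | 27.2% |
| 21 | 5% | 65.9% | 23.2% | 41.2% | 55.2% |

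Worked line: *f* = 2%, *q* = 50%, *k* = 21 gives 1 − 0.99^21 = 19.0%.

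With *k* = 6, the chance of any fed draw is 1 − 0.99^6 = 5.9%, 1 − 0.98^6 = 11.4% and 1 − 0.95^6 = 26.5%. With *q* = 50%, the chance of a false shift is 1 − 0.995^6 = 3.0%, 1 − 0.99^6 = 5.9% and 1 − 0.975^6 = 14.1%.

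The value 21 assumes all 48 cycles, while the protocol synopsis expects most participants to receive between 3 and 48. Over C2 to C13 alone (8 draws), the chance of any fed draw is 7.7%, 14.9% and 33.7%. If fed draws cluster in the same participants, fewer participants are affected than these figures suggest.

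If the maximum is taken only over samples not recorded as fed, a recorded fed draw cannot set the category.

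**The case against.** The strongest case against is that little depends on this table. The primary endpoint is adverse events, so hyperglycemia judged to be an adverse event is captured and CTCAE-graded independently. The study is single-arm and descriptive, and no decision rule uses the shift table. SAP 4 allows further tables. This stands, and it limits the weight of the point.

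A fasting-only table would also remove observed high glucose values from a safety display. That is fair, and it is why the all-samples version should be shown alongside.

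Several stronger readings are tempting, but the documents do not support them:
- *That the SAP declares fed samples to be fasting.* It does not; it is silent and pools them.
- *That lipid shift tables are affected.* There are none. Lipids are affected only in by-cycle values and change from baseline.
- *That 19%, 35% and 66% are misclassification rates.* They are the chance of any fed draw over a full schedule. A false shift also needs the fed value to exceed ULN while all scheduled fasting values do not.
- *That a fed baseline will often hide a real shift.* This is possible under SAP 4.2.2, but the baseline chemistry is normally the screening sample, where Protocol 3.2 judges fasting glucose for eligibility. A later fasting repeat before first dose would replace a fed value.
- *That the 4-hour and 8-hour rules bias age groups differently.* Different fasting times do not imply different fed rates, and SAP 4.17 has no laboratory tables by age.

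Finally, the eCRF itself is not among the documents. SAP 7 reports that eCRF data could not support another planned calculation, so the fed field should be checked before it is relied on.

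**Conclusion.** The point holds for glucose and insulin in both the by-cycle summaries and the shift tables, and for lipids in the by-cycle summaries only. Applying SAP 4.17 and 4.3.7 as written can put a participant in the wrong glucose category when a correct fasting value is on file.

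The size is uncertain, because the fed rate and the chance that a fed value exceeds ULN are both assumed. With *q* = 50% and fed rates of 1% to 2%, the false-shift rate among participants with normal fasting values is 10% to 19% with 21 draws and 3% to 6% with 6. Shorter treatment or clustering of fed draws lowers these figures. The correction is worth making because it is cheap and the table is the SAP's only categorical laboratory view of glucose. It does not threaten the primary adverse event analysis.

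**What to change.** In SAP 4.17, with a cross-reference from 4.2.2 and 4.3.7:
1. Derive baseline and change from baseline for glucose, insulin and lipids, and the minimum and maximum shifts for glucose and insulin, from samples not recorded as fed.
2. Let a fasting repeat at the same visit replace a fed scheduled value, as a stated exception to 4.3.7.
3. Flag fed values in the laboratory listings.
4. Show an all-samples version of the same tables alongside, so that no high value is hidden.
5. State which Table 3 row supplies the glucose and insulin values, and confirm that the fed field exists on the eCRF.

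The cost is a few sentences, a filter on a record the protocol already asks for, one extra set of tables, and slightly fewer values in the fasting tables. No new data are needed.

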#### 5.4 Pharmacokinetic Assessments

With Amendment 7, PK analyses will be limited to data already collected, as additional PK samples will not be collected.

PK variables measured will include  $C_{max}$ ,  $T_{max}$ , and AUC.

For Part A, blood samples for PK analysis will be collected during Cycle 1 on Day 1 and Day 15 and on Cycle 2 Day 1 (Annex 1). Blood samples for PK analysis will also be collected during Cycles 4 and 7. If the dose did not increase during Cycle 4 or Cycle 7, a

single PK sample will be collected on Day 1 of these cycles. If the dose did increase during Cycle 4 or Cycle 7, blood samples for PK analysis will be collected on Day 1 and Day 15, and a single PK sample will be collected on Cycle 5 Day 1 and Cycle 8 Day 1. The blood sampling date and time and the time of dosing of miransertib administration on the days of PK collection must be recorded on the eCRF.

For Part B (Cohorts 1, 2, and 3), blood samples for PK analysis will be collected during Cycles 1 and 4 according to the schedule in Table 2. The blood sampling date and time and the time of dosing of miransertib administration on the days of PK collection must be recorded on the eCRF.

Table 2 Part B: PK Sampling Schedule (Cohorts 1, 2, and 3)

Day	Procedure	Collection Timepoint	Permitted Window for blood draw
CYCLE	1 and CYCLE 4 Day 1		
Draw blood sample		0 hour (before the first dose of miransertib)	NA
1	Draw blood sample	3 hours	(± 15 minutes)
1	Draw blood sample	8 hours	(± 1 hour)
CYCLE	1 and CYCLE 4 Day 15		
1	Draw blood sample	0 hour (before dosing)	NA
1	Draw blood sample	4 hours	(± 15 minutes)
1	Draw blood sample	6 hours	(± 1 hour)

NA=not applicable

Detailed instructions for collection and shipment of plasma PK samples will be provided in the Laboratory Manual. Samples for PK assessments will be labeled by personnel from the institution with the participants' study ID; the participants' identity will not be made known to employees from the Sponsor, additional collaborators, or other Investigators. Samples will only be used for the purposes of the protocol and will only be used by the Sponsor's personnel or by an external laboratory chosen by the Sponsor to outsource the analyses according to internal guidelines. Samples will be kept until all protocol-related analyses are completed, for a period not exceeding 10 years or as required by local law.

## 5.5 Other Assessments

A single blood sample will be collected from all participants for detecting polymorphism of CYP2D6. The goal will be to explore the impact of these variants on study endpoints as well as on PK. This may only be explored for participants enrolled before Amendment 7.

## 5.6 Additional Tests

No longer applicable with the adoption of Amendment 7.

## 5.7 Home Blood Glucose Monitoring

At home, fasting glucose measurements may be performed as necessary in case of symptoms or as determined by the investigator.

## 5.8 Schedule of Events

## 5.8.1 Cohorts 1, 2, and 3

Table 3 is intended as a list of visits and associated assessments. Please refer to relevant protocol sections for detailed information.

Table 3 Schedule of Events Part B Cohorts 1, 2 and 3

Phase	Screening	Screening Treatment (Year 1) 1						Follow	Follow-Up	
Tests & Procedures / Visit Name	Screening	C1D1	C1D15 C4D15	C2, C3, C5, C9, C11,	C4D1	C7, C13	C16, C19, C22, C25, C28, C31, C34, C37, C40, C43, C46	EOT (C48)	30-day Safety Follow-up	
Window (days)	-14 to 0	-1 to 0	± 3	± 5		± 5	± 5	Within 7 days	30+ Days	
Written informed consent	X									
Medical history	X									
Physical examination	X	X	X	X	X	X	X	X	X	
Vital signs	X	X	X	X	X	X	X	X	X	
Calculate BSA / dose		X		X	X	X	X			
Dose increase to 25 mg/m 					X					
12-lead ECG		X	X		X			X	X	
Fasting clinical blood tests	X			X	X	X	X	X	X	
Insulin/glucose blood tests	X					X	X (C19, C25, C37)	X		
Urinalysis	X			X	X	X	X	X	X	
Serum pregnancy test (if applicable)	X							X	X	
Dispense study medication 		X		X	X	X	X			
Collect and count returned miransertib capsules				X	X	X	X	X		
Concomitant medications	X	X	X	X	X	X	X	X	X	
Adverse events		X	X	X	X	X	X	X	X	

BSA=body surface area; C=cycle; D=day; ECG=electrocardiogram; EOT=end of treatment.

The following CXDX visit assessments may be performed within a 24-hour window of dosing (Physical Examination, ECG)

Dispense monthly allotments at C1, C2, C3, C4; 2-month allotments at C5, C7, C9, C11; 3-month allotments at C13, C16, C19, C22, C25, C28, C31, C34, C37, C40, C43; 2-month allotment at C46

## **5.8.2** Cohort 4

Table 4 is intended as a list of visits and associated assessments. Please refer to relevant protocol sections for detailed information.

